6.5.2.1.2 Dose adjustments of ruxolitinib for non-hematologic safety

Dose reductions or interruptions for non-hematologic toxicity are permitted in order to allow the patient to continue on the study treatment. Dose adjustments for different ranges of non-hematologic toxicity are described in [Table 6-3](#). The objective of the dose adjustment rules is to optimize treatment response for each individual patient while avoiding significant non-hematologic toxicities.

As organ toxicities are relatively common in alloSCT patients, any AE must be assessed to determine whether it is suspected to be related to ruxolitinib treatment. Ruxolitinib dose adjustments are only required for AEs that are suspected to be related to the study drug. This has particular relevance in evaluation of elevated creatinine, as elevations related to CNI administration are often seen. Dose adjustment of CNI will follow institutional guidelines and investigator judgement, with CNI dose reductions anticipated if rising creatinine noted, to potentially alleviate the need for ruxolitinib dose reductions.

Ruxolitinib must be permanently discontinued upon any one of the following non-hematological AEs attributed to study drug that fails to resolve to Grade 2 or better within 14 days, or if a lower re-start dose or administration schedule subsequent to any of the following non-hematologic toxicities is either not available or likely to be clinically ineffective:

1. The occurrence of a Grade 4 laboratory or non-laboratory abnormality attributable to ruxolitinib;

2. The occurrence of a Grade 3 laboratory or non-laboratory abnormality attributable to ruxolitinib that remains at Grade 3 or worse for greater than 14 days.

If any one or more of the treatment discontinuation criteria outlined above are met prior to Day 28, the patient will be considered to be a non-responder in terms of the Day 28 primary endpoint. Subsequent to Day 28, if any one or more of the treatment discontinuation criteria outlined above are met, the patient will be considered to be a non-responder in terms of the Day 56 secondary endpoint.

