12.5 Analysis of secondary endpoints

12.5.1 Efficacy and/or Pharmacodynamic endpoint(s)

The main secondary objective of the study is to estimate the proportions of all patients who achieve a complete response (CR) or partial response (PR) at Day 28 and maintain a CR or PR at Day 56. A patient will not be considered a durable responder at Day 56 if any of the following events occurs prior to or at Day 56:

- No CR or PR at Day 28 or at Day 56.
- aGvHD progression or additional systemic therapy for aGvHD

The durable response rates for ORR at Day 56 will be estimated with 90% confidence intervals on EES. Summary statistics (frequencies and percentages). The confidence intervals will be calculated based on the exact method for binomial distribution.

All secondary efficacy endpoint analyses will be analyzed using the EES.

- Overall Response Rate at Day 14, will be derived in the same way as the primary variable ORR at Day 28.
- Duration of response (DOR)

Duration of response will be calculated for patients whose overall response at Day 28 is CR or PR according to updated standard criteria ([Harris et al 2016](#)). The start date is the date of first documented response of CR or PR (i.e., the start date of response), and the end date is defined as the date of progression or the date of addition of systemic therapies for aGvHD, since this constitutes a non-response.

Death without prior observation of aGvHD progression and onset of chronic GvHD are considered to be competing risks.

Duration of response will be censored at the last response assessment prior to or at the analysis cut-off date, if no events/competing risk occurred before or at of cut-off date.

DOR will be listed and summarized for all patients on the EES with overall response of CR or PR at Day 28.

- Overall survival (OS)

Overall survival is defined as the time from date of the start of study treatment to date of death due to any cause. If a patient is not known to have died, then OS will be censored at the latest date the patient was known to be alive (on or before the cut-off date).

The OS distribution will be estimated using the Kaplan-Meier method, and the Kaplan-Meier curves, medians, 1, 2, 6, 12, 18 and 24 month survival estimates and 95% confidence intervals will be presented.

- Event Free Survival (EFS)

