3.5.3 Handling of missing values/censoring/discontinuations

Patients with missing assessments that prevent the evaluation of the ORR will be considered non-responders. This includes aGvHD response assessments at baseline and Days 28, 56. Patients who discontinue the study treatment prior to the completion of the Day 28 visit will be considered non-responders.

The following analysis windows will be applied to the target day for assessments on overall response, where target day for Week X is X*7.

Baseline assessment is the last aGvHD assessment prior to or at the start of study treatment (Day 1).

Weeks 1, 2, 3, 4, 5, 6, 7, 8: -3 days/+3 days

Weeks 12 to 48: -13 days/+14 days

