3.6 Analysis of the key secondary objective

3.6.1 Key secondary endpoint

The key secondary objective of the study is durable ORR at Day 56.

Durable ORR at Day 56 is defined as the proportions of all patients who achieve a complete response (CR) or partial response (PR) at Day 28 and maintain a CR or PR at Day 56. If a patient is a CR at Day 28 and a PR at Day 56, he/she will be considered as a durable responder. A patient will not be considered a durable responder at Day 56 if any of the following events occurs:

- Not responder at Day 28
- Missing aGvHD assessment at Day 56
- No CR or PR at Day 56.
- additional systemic therapy for aGvHD prior to Day 56

Durable ORR will be calculated based on the FAS using local investigators review of aGvHD assessment data.

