3.7.3 Handling of missing values/censoring/discontinuations

Patients with missing assessments that prevent the evaluation of the ORR at Day 14 will be considered non-responders. This includes missing aGvHD assessments at baseline and/or Day 14. The time window for the Day 14 visit is defined in [Section 2.5.3](#).

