Sample size	Minimum No. of responders	Response Rate	Probability to have a 90% CI with lower limit $\geq 60\%$	90% CI	
37	28	0.76	0.809	0.614	0.867
38	29	0.76	0.784	0.623	0.871
39	29	0.74	0.859	0.604	0.854
40	30	0.75	0.839	0.613	0.858
41	31	0.76	0.818	0.621	0.861
42	31	0.74	0.882	0.604	0.846
43	32	0.74	0.864	0.612	0.849
44	33	0.75	0.846	0.620	0.853
45	33	0.73	0.901	0.604	0.838
46	34	0.74	0.886	0.612	0.842
47	35	0.74	0.869	0.619	0.846
48	35	0.73	0.916	0.604	0.832
49	36	0.73	0.903	0.612	0.835
50	37	0.74	0.889	0.619	0.838

5 Change to protocol specified analyses

No change from protocol

6 Appendix

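### Protocol 6.5.2.1.2 makes qualifying toxicity after Day 28 a Day 56 non-response, but Protocol 12.5.1 and the SAP do not, so durable ORR has two conflicting definitions

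*SAP*

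**What the plan says.** Protocol 6.5.2.1.2 is a dose-adjustment section, but it also classifies endpoints. Its trigger begins: "Ruxolitinib must be permanently discontinued upon any one of the following non-hematological AEs attributed to study drug that fails to resolve to Grade 2". Improvement at least to that grade has to come inside a 14-day limit; the alternative condition is that no usable lower re-start dose or schedule exists. The listed events are a Grade 4 abnormality attributable to ruxolitinib, and a Grade 3 abnormality attributable to ruxolitinib that lasts more than 14 days. Two paired consequences follow. If the criteria are met before Day 28, "the patient will be considered to be a non-responder in terms of the Day 28 primary endpoint". If they are met after Day 28, "the patient will be considered to be a non-responder in terms of the Day 56 secondary endpoint".

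SAP 3.6.1 introduces its durable-ORR failures with "A patient will not be considered a durable responder at Day 56 if any of the following events occurs" and lists four. Stopping treatment is not one of them, and neither is toxicity. SAP 3.6.3 only refers back to the Day 28 missing-data section (it cites the old number 2.5.3; by content this is 3.5.3). The stopping rule there is: "Patients who discontinue the study treatment prior to the completion of the Day 28 visit will be considered non-responders".

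The protocol's statistical text has the same gap. Section 12.4.3 gives the same Day 28 stopping rule as SAP 3.5.3. Section 12.5.1 defines durable-response failure as no CR or PR at Day 28 or Day 56, aGvHD progression, or additional systemic therapy. SAP section 5, on changes to protocol-specified analyses, states: "No change from protocol".

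**The concern.** The two halves of the 6.5.2.1.2 rule are treated differently. The Day 28 half is covered, because SAP 3.5.3 fails anyone who stops for any reason before the Day 28 visit is complete. The Day 56 half appears in no analysis text. Two programmers working from the governing documents could produce different numerators for the key secondary endpoint, and the SAP gives no sign that a choice was made.

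What is at stake is the meaning of a durable response. Under one rule, a response that is still present at Day 56 after ruxolitinib was stopped for serious attributed toxicity counts as a success. Under the other it counts as a failure.

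**Working it through.** **1. The plan's own figure.** The only efficacy precision figure is for Day 28 ORR (Protocol Table 12-2, SAP Table 4-1). With n = 45, the smallest r whose two-sided 90% Clopper-Pearson lower limit, the 0.05 quantile of Beta(r, 46 − r), is at least 0.60 is r = 33. Its interval is 0.604 to 0.838. With a true ORR of 0.80, P(X ≥ 33) for X ~ Bin(45, 0.80) is 0.901. All three match the plan. They are not in dispute; they only confirm the interval method used in step 5. The plan gives no corresponding figure for durable ORR.

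**2. The failure rules side by side.**

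| Event | Protocol 6.5.2.1.2 | Protocol 12.4.3 / 12.5.1 | SAP 3.5.3 / 3.6.1 / 3.6.3 |
|---|---|---|---|
| Stops before the Day 28 visit is complete | Toxicity criteria met before Day 28 | Yes, any reason | Yes, any reason |
| Toxicity criteria met after Day 28 | Day 56 non-responder | Not listed | Not listed |
| No CR/PR at Day 28 or Day 56 | – | Yes | Yes |
| Day 56 assessment missing | – | Yes | Yes |
| Additional systemic aGvHD therapy | – | Yes | Yes |
| aGvHD progression by Day 56 | – | Yes | Not listed |

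**3. Can a patient fall in the gap?** Yes.
- Protocol 8.4.1.2 continues disease assessments weekly to Day 56 in patients withdrawn from treatment, so an off-drug Day 56 CR or PR will be on file.
- Protocol 6.5.2.1.3 allows corticosteroids to manage the flare that is expected when ruxolitinib stops.
- SAP 6.4.3 says that changes in systemic corticosteroids are never new or additional therapy, so the fourth SAP failure event does not catch this patient.

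Take a Day 28 responder with a non-hematologic Grade 4 event attributed to ruxolitinib. It does not improve to Grade 2 within 14 days, and on Day 35 the patient meets the criteria and stops. The patient starts no new systemic therapy and is in CR at Day 56. The SAP counts a durable responder; Protocol 6.5.2.1.2 counts a non-responder.

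**4. Direction.** Adding a failure event can only remove patients from the numerator. The SAP rate is therefore at least the 6.5.2.1.2 rate, and equal to it if nobody qualifies.

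**5. Size.** One patient is 1/45 = 2.2 percentage points. The number of affected patients, k, is not in the documents, so it is an assumed range of 0 to 5, giving 0 to 5/45 = 11.1 points. The base rates are also assumptions. The first, 40%, is the ruxolitinib arm's durable response in the phase III trial in steroid-refractory patients aged 12 or older (Protocol 1.1.2.1.2). The second is a higher value for contrast.

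| Base under the SAP rule | k = 0 | k = 2 | k = 5 |
|---|---|---|---|
| 18/45 | 40.0% (27.7 to 53.3) | 16/45 = 35.6% (23.7 to 48.9) | 13/45 = 28.9% (18.0 to 42.0) |
| 30/45 | 66.7% (53.4 to 78.2) | 28/45 = 62.2% (48.9 to 74.3) | 25/45 = 55.6% (42.3 to 68.3) |

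Parentheses are exact 90% intervals. With k = 2 the shift is 4.4 points, well inside the width of either interval.

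**The case against.** The strongest reply is that the SAP follows the protocol where it should. Its discontinuation rule repeats 12.4.3, its failure list resembles 12.5.1, and Protocol Table 2-1 defines the endpoint simply as CR or PR at Day 28 maintained at Day 56. Counting observed Day 56 status whether or not ruxolitinib was stopped is a legitimate estimand. On this reading, a stray sentence in a dosing section does not override the statistical section. This stands in part: the conflict lies inside the protocol as much as between protocol and SAP. It does not cancel the sentence in 6.5.2.1.2, which names the endpoint and the classification outright.

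The affected group is also narrow. A patient must respond at Day 28, first meet the criteria between Days 28 and 56, start no new systemic therapy, and still be in response although flare is expected after abrupt stopping. Zero is plausible. A reader might take the 4 of 11 toxicity failures in the retrospective pediatric series (Protocol 1.1.2.1.2) as a guide to the number. The documents do not support that. Those children were counted separately from the responders, the reported toxicities included neutropenia and thrombocytopenia, no Day 28 to 56 timing is given, and the protocol itself says their disease was much more advanced.

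No hypothesis is tested and no threshold is set for durable ORR, so no formal conclusion turns on the choice.

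**Conclusion.** The inconsistency is real and should be fixed, although it threatens neither the primary endpoint nor any test. Durable ORR has two conflicting definitions, and SAP section 5 is silent on the choice. If any patient qualifies, the SAP rate exceeds the 6.5.2.1.2 rate by 2.2 points each, assuming the planned 45 evaluable patients as denominator. How many qualify is unknown.

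Three stronger readings are not supported:
- **That the SAP alone dropped a protocol rule and its estimate is biased upward.** Protocol 12.4.3 and 12.5.1 lack the rule too, and the documents do not establish which definition is the target. What is shown is a one-directional difference between two rules.
- **That any stop between Day 28 and Day 56 is a non-response.** The rule covers only non-hematologic, ruxolitinib-attributed events that meet the grade, duration and re-start conditions. Hematologic and other reasons for stopping are outside it.
- **That a required stopping rule is also missing for Day 14.** Protocol 12.5.1 says "Overall Response Rate at Day 14, will be derived in the same way as the primary variable ORR at Day 28", and SAP 3.7.3 carries only "Patients with missing assessments that prevent the evaluation of the ORR at Day 14 will be considered non-responders". Inferring a stopping rule from the first sentence is possible, but the text does not say it. This is a separate, minor clarification.

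**What to change.** Decide before database lock, since the SAP introduction says that all final-analysis decisions are made by then.

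**Option A.** Add to SAP 3.6.1, and align Protocol 12.5.1 with, the failure event: *met the treatment discontinuation criteria of Protocol 6.5.2.1.2 after Day 28 and up to Day 56*. Derive it from AE grade, relationship to ruxolitinib, hematologic or non-hematologic status and event dates, together with the permanent-discontinuation record. A blanket discontinuation flag from the treatment CRF would wrongly include hematologic and other stops. Date the event by when the criterion is met, not by AE onset, because a Grade 3 event qualifies only after more than 14 days. Report observed Day 56 status regardless of stopping as a supplementary line.

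**Option B.** Keep the SAP list, remove the Day 56 sentence from Protocol 6.5.2.1.2, and record the choice in SAP section 5.

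With either option, reconcile aGvHD progression by Day 56, which Protocol 12.5.1 lists and SAP 3.6.1 omits. Correct the cross-reference in SAP 3.6.3, and state separately whether stopping before the Day 14 visit is a non-response.

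The cost of A is one derived variable from data already collected, one extra table row and a possibly slightly lower durable ORR. The cost of B is wording only. Neither changes how patients are treated.

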3.6.2 Statistical hypothesis, model, and method of analysis

The durable response rates for ORR at Day 56 will be estimated with 90% confidence intervals on EES. Summary statistics (frequencies and percentages). The confidence intervals will be calculated based on the exact method for binomial distribution.

3.6.3 Handling of missing values/censoring/discontinuations

Refer to [Section 2.5.3](#)

3.7 Analysis of secondary efficacy objective(s)

3.7.1 Secondary endpoints

- **Overall Response Rate at Day 14**

Overall Response Rate at Day 14 is defined as the proportion of patients with complete response (CR) or partial response (PR) at Day 14 according to standard criteria [\[Harris 2016\]](#).

- **Duration of response (DOR)**

Duration of response will be calculated for patients whose overall response at Day 28 is CR or PR according to updated standard criteria [\(Harris et al 2016\)](#). The start date is the date of first documented response of CR or PR (i.e., the start date of response), which could be prior to or at Day 28. If it's prior to Day 28, there should not be progression or addition of systemic therapies for aGvHD between the start date of response and Day 28. The end date is defined as the date of progression or the date of addition of systemic therapies for aGvHD on or after Day 28, since this constitutes a non-response. The date of progression will be the earliest date of PD recorded in the aGvHD assessment CRF page or the date of death due to aGvHD in the death CRF page.

Death without prior observation of aGvHD progression (i.e. date of death due to non aGVHD reason (Other) in the death CRF page) and onset of chronic GvHD are considered to be competing risks.

Duration of response will be censored at the last response assessment prior to or at the analysis cut-off date, if no events/competing risk occurred before or at of cut-off date.

- **Best Overall Response**

Best overall response (BOR) is defined as proportion of patients who achieved overall response (CR or PR) at any time point up to and including Day 28 and before the start of additional systemic therapy for aGvHD.

An additional analysis will include BOR at any time point up to the data cut-off date and before the start of additional systemic therapy for aGvHD. A swimmer plot for overall response by age group, SR-aGvHD vs Treatment Naive and formulation will also be provided for all treated subjects.

- **Overall survival (OS)**

Overall survival is defined as the time from date of the start of study treatment to date of death due to any cause. If a patient is not known to have died, then OS will be censored at the latest date the patient was known to be alive (last contact date on or before the cut-off date).

- **Event Free Survival (EFS)**

Event-free survival is defined as the time from the study treatment start date to the date of hematologic disease relapse/progression, graft failure or death due to any cause. If a patient is not known to have any event, then EFS will be censored at the latest date the patient was known to be alive (last contact date on or before the cut-off date).

- **Failure Free Survival (FFS)**

Failure-free survival is defined as the time from the study treatment start date to date of hematologic disease relapse/progression, non-relapse mortality (NRM) or addition of new systemic aGvHD treatment. Each type of failure as a competing risk for the other two, and onset of chronic GvHD is considered as a competing risk for all three types of failure. If a patient is not known to have any event or competing risk, then FFS will be censored at the latest date the patient was known to be alive (last contact date on or before the cut-off date).

- **Non-relapse mortality (NRM)**

Non-relapse mortality is defined as the time from the study treatment start date to date of death not preceded by hematologic disease relapse/progression. Hematologic disease relapse/progression is considered a competing risk for NRM with the date of hematologic disease relapse/progression being the earlier of documented hematologic disease relapse/progression or institution of therapy to treat potential hematologic disease relapse/progression. If a patient is not known to have died or to have relapsed/progressed, then NRM will be censored at the latest date the patient was known to be alive (last contact date on or before the cut-off date).

- **Incidence of Malignancy Relapse/Progression (MR)**

Malignancy relapse/progression is defined as the time from the study treatment start date to date of hematologic malignancy relapse/progression. Deaths not preceded by hematologic

malignancy relapse/progression are competing risks. If a patient is not known to have event or competing risks, then MR will be censored at the latest date the patient was known to be alive (last contact date on or before the cut-off date).

- **Cumulative steroid dosing until Day 56**

The weekly cumulative steroid dose will be calculated for each patient up to Day 56 and the overall cumulative steroid dose will be calculated for each patient at Day 56. In addition, the proportion of patients with any dose reduction and any dose reduction of at least 50% in corticosteroids from baseline until EOT will be provided.

- **Incidence of cGvHD**

cGvHD is defined as the diagnosis of any cGvHD including mild, moderate, severe. Incidence of cGvHD is the time from the start of treatment to onset of cGvHD. Cumulative incidence of cGvHD will be estimated, accounting for deaths without prior onset of cGvHD and hematologic disease relapse/progression as the competing risks. If a patient is not known to have event or competing risks, then the incidence of cGvHD will be censored at the latest date the patient was known to be alive (last contact date on or before the cut-off date).

- **Graft failure**

This will be assessed by donor cell chimerism, defined as initial whole blood or marrow donor chimerism for those who had $\geq 5\%$ donor cell chimerism at baseline. If donor cell chimerism declines to $< 5\%$ on subsequent measurements, graft failure is declared.

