8.4 Efficacy

8.4.1 Staging and Response assessments

8.4.1.1 aGvHD staging

Organ staging of aGvHD will be performed according to updated NIH criteria as described by [Harris et al 2016](#) in the table below.

■

Table 8-2 Acute GvHD Staging Criteria (Harris et al 2016)

Stage	Skin (Active Erythema Only)	Liver (Bilirubin)	Upper GI	Lower GI (stool output/day)
Stage 0	No active (erythematous) GVHD rash	< 2mg/dL	No or intermittent nausea, vomiting, or anorexia	Adult: <500mL/day or < 3 episodes/day Child: <10mL/kg/day or < 4 episodes/day
Stage 1	Maculopapular rash < 25% BSA	2 – 3 mg/dL	Persistent nausea, vomiting, or anorexia	Adult: 500-999 mL/day or 3-4 episodes/day Child: 10-19.9 mL/kg/day or 4-6 episodes/day
Stage 2	Maculopapular rash < 25-50% BSA	3.1 – 6 mg/dL		Adult: 1000-1500mL/day or 5-7 episodes/day Child: 20-30mL/kg/day or 7-10 episodes/day
Stage 3	Maculopapular rash > 50% BSA	6.1 – 15 mg/dL		Adult: >1500mL/day or > 7 episodes/day Child: >30mL/kg/day or > 10 episodes/day
Stage 4	Generalized erythroderma (>50% BSA) plus bullous formation and desquamation > 5% BSA	> 15 mg/dL		Severe abdominal pain with or without ileus or grossly bloody stool (regardless of stool volume)

Overall clinical grade (based on most severe target organ involvement):

Grade 0: No stage 1-4 of any organ.

Grade I: Stage 1-2 skin without liver, upper GI or lower GI involvement.

Grade II: Stage 3 rash and/or stage 1 liver and/or stage 1 upper GI and/or stage 1 lower GI.

Grade III: Stage 2-3 liver and/or stage 2-3 lower GI with stage 0-3 skin and/or stage 0-1 upper GI.

Grade IV: Stage 4 skin, liver or lower GI involvement, with stage 0-1 upper GI.

8.4.1.2 aGvHD assessment

aGvHD grading will be performed by the investigator on a weekly basis for the first 8 weeks after treatment assignment and then every 28 days thereafter during the treatment period and at EOT visit as outlined in [Table 8-1](#).

aGvHD assessment will be performed as per [Table 8-2 \(Harris et al 2016\)](#): organ assessment (skin; liver; upper GI; Lower GI) and overall grading at the time of the evaluation should be reported according to [Table 8-2](#).

In addition, biopsy of the organ involved may be performed per institutional practices at investigator's discretion for aGvHD management. If performed, the investigator will indicate the results once available.

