Response to study treatment will be assessed by the investigator at every visit during the treatment period ([Section 8.3](#)). Response assessment by the investigator at Day 28 and at Day 56 will support respectively, the primary and key secondary endpoint assessments for this trial.

Patients will be also monitored for aGvHD flares occurring during steroid, CNI, and ruxolitinib taper.

Investigator should carefully record any action taken to manage aGvHD including start of tapering, initiation of any new systemic therapy, re-escalation of corticosteroids and the re-escalated steroid dose, and steroid taper failure.

The data should be entered in the appropriate CRFs. Worsening of aGvHD, including occurrence of GvHD flare will be reported on appropriate specific CRF and, not as an adverse event ([Section 10.1.1](#)).

Note: Additional assessments may be done as per institutional guidelines at investigator's discretion. aGvHD assessments performed at unscheduled visit and leading to a change in patient's management or a change in patient's response should be recorded in the CRF.

Table 8-3 Response assessment

Efficacy assessments:

aGvHD response assessment will be made with respect to the organ stage at screening and Day 1:

4. **Complete response** is defined as a score of 0 for the aGvHD grading in all evaluable organs that indicates complete resolution of all signs and symptoms of aGvHD in all evaluable organs without administration of additional systemic therapy for any earlier progression, mixed response or non-response of aGvHD.
5. **Partial response** is defined as improvement of 1 stage in 1 or more organs involved with aGvHD signs or symptoms without progression in other organs or sites without administration of additional systemic therapy for an earlier progression, mixed response or non-response of aGvHD.
6. **Lack of response** is defined as no response, mixed response, or progression.
7. **No response** is defined as absence of improvement in any organ involved by aGvHD, without worsening in any involved organ.
8. **Mixed response** is defined as improvement of at least 1 stage in the severity of aGvHD in one organ accompanied by progression in another organ or development of signs or symptoms of aGvHD in a new organ.
9. **Progression** is defined as worsening in 1 or more organs by 1 or more stages without improvement in any involved organ.

Patients requiring additional systemic therapy for aGvHD will be classified as non-responders.

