3.5.1 Primary endpoint

The primary endpoint of the Phase I is the list of following PK parameters (AUC, Cmax, T1/2, Ctrough, and other parameters, as appropriate) which will be derived using non-compartmental methods in subjects with extensive sampling (Groups 1, 2, and 3). These parameters will then be used to define a RP2D for Groups 2, 3, and 4. The observed PK parameters (within group) will be summarized and compared to information obtained from adult and adolescent aGvHD patients treated with ruxolitinib on study CINC424C2301. Data from patients older than 2 years old will be combined and analyzed by PBPK methods to determine the dose to be administered in patients younger than 2 years old (Group 4).

The primary endpoint for the Phase II is the investigator-reported overall response rate (ORR) at Day 28, defined as the proportion of patients with complete response (CR) or partial response (PR) without requirement for additional systemic therapies for an earlier progression, mixed response or non-response as per [Table 8-3](#) of the protocol ([Harris et al 2016](#)). Note that response is relative to the assessment of aGvHD at the start of study treatment.

- **Complete-response** is defined as a score of 0 for the aGvHD grading in all evaluable organs that indicates complete resolution of all signs and symptoms of aGvHD in all evaluable organs without administration of additional systemic therapies for any earlier progression, mixed response or non-response of aGvHD.
- **Partial response** is defined as improvement of 1 stage in 1 or more organs involved with aGvHD signs or symptoms without progression in other organs or sites without administration of additional systemic therapies for an earlier progression, mixed response or non-response of aGvHD.
- **Lack of response** is defined as no response, mixed response, or progression.
- **No response** is defined as absence of improvement in any organ involved by aGvHD, without worsening in any involved organ.
- **Mixed response** is defined as improvement of at least 1 stage in the severity of aGvHD in at least one organ accompanied by progression in another organ or development of signs or symptoms of aGvHD in a new organ.
- **Progression** is defined as worsening in 1 or more organs by 1 or more stages without improvement in any involved organ

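### DOR has no end event for a Day 28 responder who falls to no response or mixed response without new therapy, so it can understate loss of response; one sensitivity analysis would show by how much

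*SAP*

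**What the plan says.** **DOR.** SAP 3.7.1 defines DOR for patients in CR or PR at Day 28. It ends at progression or at added systemic therapy, the latter "since this constitutes a non-response". Progression is dated as follows: "The date of progression will be the earliest date of PD recorded in the aGvHD assessment CRF page", or the date of death from aGvHD. Other deaths and onset of chronic GvHD are competing risks. Everyone else is censored at the last response assessment. SAP 3.7.2 reports cumulative incidence at 1, 2, 6, 12, 18 and 24 months. Protocol Table 2-1 and 12.5.1 give the same end events, except that dating progression by aGvHD death is specified only in the SAP.

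**Response categories.** In SAP 3.5.1, lack of response "is defined as no response, mixed response, or progression". Progression is "worsening in 1 or more organs by 1 or more stages without improvement in any involved organ". Protocol Table 8-3 describes mixed response as "improvement of at least 1 stage in the severity of aGvHD in one organ accompanied by progression in another organ", or a newly involved organ. The reference point is fixed: "Note that response is relative to the assessment of aGvHD at the start of study treatment".

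**Durable ORR.** SAP 3.6.1 lists "No CR or PR at Day 56" among the reasons a patient is not a durable responder.

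**Managing a flare.** Protocol 6.1.5.1.1 allows steroid re-escalation before Day 56 and a return to a higher ruxolitinib dose after it. SAP 6.4.3 excludes corticosteroid changes from new therapy, and a ruxolitinib dose change is not among the sources it searches.

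**Other analyses.** The one named sensitivity analysis (SAP 3.5.4) removes patients with assessment deviations at Day 28. SAP 3.7.1 also plans a swimmer plot of overall response.

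**The concern.** Once a child has responded, the clinical question is when that response is lost. The SAP answers it with only one of its three lack-of-response categories, plus new therapy and aGvHD death. Because the comparison is with treatment start and not with best response, a full flare back to the starting stage is not progression. Nor is severe disease in a new organ, as long as the first organ is still better than on Day 1.

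New therapy does not close the gap, because the dose increases the protocol allows for a flare do not count as new therapy. Such a child stays at risk on the DOR curve with no event, and is censored at the last assessment if nothing else happens. A reader of the curve would take loss of response to be rarer, or later, than the investigators' own response scores show. At Day 56 the curve could also disagree with the key secondary endpoint for the same child, and no planned estimate would let the reader reconcile the two.

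**Working it through.** **1. Classing under SAP 3.5.1 and Protocol Tables 8-2 and 8-3.** Stages are (skin, lower GI), with no other organ involved. The child is a Day 28 responder, the status shown is that at Day 56, and only the steroid dose has been raised.

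| Day 1 | Day 28 | Day 56 | Category at Day 56 | Durable ORR | DOR event |
|---|---|---|---|---|---|
| 3, 0 | 0, 0 (CR) | 3, 0 | No response | Fails | No |
| 3, 0 | 0, 0 (CR) | 0, 4 | Mixed response | Fails | No |
| 3, 3 | 0, 0 (CR) | 0, 4 | Mixed response | Fails | No |
| 3, 0 | 0, 0 (CR) | 4, 0 | Progression | Fails | Yes |
| 3, 0 | 0, 0 (CR) | 3, 1 | Progression | Fails | Yes |

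- Row 2 goes from grade II on Day 1 to the worst overall grade: "Grade IV: Stage 4 skin, liver or lower GI involvement, with stage 0-1 upper GI". It is still not progression, because the skin is improved.
- In row 3 the lower GI tract is worse than on Day 1 and there is still no event. The fixed reference point is therefore not the only cause; the requirement that no organ be improved also matters.
- Row 5 is a new-organ flare that does end DOR, because no organ is improved.

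**2. Number of responders.** The plan states no figure for DOR. Its Day 28 figure reproduces: P(X ≥ 33 | n = 45, p = 0.80) = 0.9005, against 0.901 in Protocol Table 12-2 and SAP Table 4-1. The exact 90% interval at 33/45 is 0.604 to 0.838, and 32/45 gives a lower limit of 0.580, so 33 is the minimum. At the assumed 80%, the expected number of responders is 0.80 × 45 = 36.

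**3. Shift per child.** With no censoring before the time point, the cumulative incidence estimate is events / n. One further counted child therefore adds 1/n:

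- n = 28 (assumed 62%, the adult phase III Day 28 rate in Protocol 1.1.2.1.2; 0.62 × 45 = 27.9): 1/28 = 3.6 points
- n = 33 (Table 12-2 minimum): 1/33 = 3.0 points
- n = 36: 1/36 = 2.8 points
- n = 40 (assumed high case): 1/40 = 2.5 points

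An Aalen-Johansen check used 36 responders, an assumed 4 counted losses and 4 competing events by day 183, and follow-up past that day for all others. It gives 4/36 = 11.1%. Counting one, two or three more children gives 5/36 = 13.9%, 6/36 = 16.7% and 7/36 = 19.4%. For scale, the exact 95% binomial interval for 4/36 is 3.1% to 26.1%.

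**4. When 1/n does not apply.** A child who later has progression, new therapy or aGvHD death by the time point is already counted there, so the shift is zero and only the event date moves earlier. Censoring also breaks the simple 1/n. Protocol Table 8-1 schedules aGvHD response assessment up to Week 48 and at end of treatment, with none at Months 12, 18 or 24. The figures in step 3 therefore should not be carried to the 12-, 18- and 24-month estimates.

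**The case against.** The strongest reply is that the rule is deliberate. Protocol 6.1.5.1.1 says steroid re-escalation for an early flare is not by itself treatment failure, and 8.4.1.2 reserves failure for flares needing new systemic therapy. The DOR definition is consistent across protocol and SAP and fits that tolerance. Two endpoints with different definitions may differ without either being wrong. Protocol 3.2 and SAP 2.2 give the task of assessing durability to the Day 56 endpoint, and that endpoint does count no response and mixed response. DOR is secondary and descriptive.

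All of this stands. It is why the planned definition should remain the main analysis and why the point is modest. It does not supply an estimate of loss of response away from Day 56 that counts all three categories; the swimmer plot may show such losses but gives no estimate.

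A reader might infer more than the documents support:

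- *That every new-organ flare is missed.* Only those with another organ still improved are missed.
- *That protocol and SAP conflict on when DOR ends.* They share the same end events; dating progression by aGvHD death is an SAP specification.
- *That the wider use of flare failure in Protocol 6.1.5.1.1 leaves the analysis undefined.* SAP 3.5.1 already ties flare failure to new systemic therapy, and no SAP endpoint uses it as an event.
- *That the adult phase III results in Protocol 1.1.2.1.2 show the gap at work.* There, 96 − 61 = 35 of 96 Day 28 responders were not durable at Day 56, while loss of response at 6 months was 10%. The protocol does not give that trial's definition of loss of response. Deaths, other competing events or missing visits could explain the whole difference, so it is not evidence here.

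**Conclusion.** The concern holds as a limit on what the DOR curve can support. A Day 28 responder can lose CR or PR, be scored no response or mixed response, and have no DOR event; at Day 56 the same child fails durable ORR. DOR can therefore understate loss of response or date it late.

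The size is unknown. The documents give no rate for this group, and it may be empty. Each affected child is worth about 2.8 points with 36 responders (2.5 to 3.6 for 40 down to 28), provided there is no later counted event by that time point and no censoring. Otherwise only the timing changes. Day 28 ORR, Day 56 durable ORR and FFS do not move, and the trial tests no efficacy hypothesis. This is a cheap improvement, not a defect that invalidates the plan.

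**What to change.** Keep the planned DOR as the main analysis. Before database lock, add one sensitivity analysis to SAP 3.7.2, using the same cumulative incidence method and the same competing risks. It would end DOR at the earliest of progression, added systemic therapy, aGvHD death, or the first assessment of no response or mixed response after Day 28.

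State its limits beside it:

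- A transient no response ends DOR early, for example at Day 42 in a child who is a durable responder at Day 56. Report how many such children there are.
- Repeat flares that remain PR against treatment start are still missed.
- Few or no such events can be seen once treatment-period visits end, because Protocol Table 8-1 schedules no aGvHD response assessment in long-term follow-up.

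The cost is one extra curve or table and one count. The investigator already assesses response at every treatment-period visit (Protocol 8.4.1.2), so no new data are needed. If no child is affected, the two curves coincide and the planned result is confirmed.
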